5.1 Randomization

Patients will be randomized 1:1 to one of the two GVHD prophylaxis regimens using blocked randomization with random block sizes. The randomization list will be generated before the start of the study by the study statistician of the study using a SAS randomization program; the list will be kept in a secured location which will only be accessible to the study coordinator. Randomization will be stratified by TBI in the preparative regimen (yes, no), donor relationship (related, unrelated), and source of hematopoietic cells (PBSC, marrow).

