14.0 STATISTICAL CONSIDERATIONS

Considering the potential for missed doses of methotrexate or other drug, this investigation will be based on an intent to treat analysis. This study hopes to show a reduction in the incidence of severe mucositis and time to neutrophil and platelet engraftment while not increasing the incidence or severity of acute GVHD in the allogeneic HCT population.

Our current rate of severe (grade 3-4) mucositis is 41%. Ninety-four (47 in each group) would be needed to demonstrate a 25% improvement in mucositis to 16%, based on a one-sided test with 5% significance and 80% power.

Our current estimate of mean day to neutrophil engraftment is 19 days. One hundred patients (50 in each group) would be needed to demonstrate a 4 day improvement in time to neutrophil engraftment based on a one-sided test with 5% significance and 80% power.

Our current percent of patients achieving platelet engraftment by day 21 is 26%. Ninety-eight (49 in each group) would be needed to demonstrate a 25% improvement in platelet engraftment to 51%, based on a one-sided test with 5% significance and 80% power.

Our current rate of any acute GVHD by day 60 is 62%. If the hazard ratio between treatment arms is at most 1.7, then we will conclude that the new treatment does not significantly increase acute GVHD. Forty-five patients per group are needed to detect this hazard ratio using a one-sided non-inferiority log-rank test with 5% significance and 80% power.

Therefore, this study requires 100 patients to have a minimum of 80% power to address all of the primary objectives.

Overall survival and progression-free survival will be estimated using the Kaplan-Meier method and compared between patients receiving Tac and MTX versus Tac, mini-MTX, and MMF using the log-rank test. Hospital stay will be compared between groups using the Wilcoxon rank sum test. TPN and 100-day incidence of complications will be compared using the Chi-square test. Acute and chronic GVHD will be estimated using cumulative incidence methods and compared using the Pepe-Mori test.

REFERENCES

1. Horan JT et al. Reducing the Risk for Transplantation-Related Mortality after Allogeneic Hematopoietic Cell Transplantation: How Much Progress Has Been Made? *JCO* 2011; 29: 805-813
2. Weisdorf D et al. Treatment of moderate/severe acute graft-versus-host disease after allogeneic bone marrow transplantation: an analysis of clinical risk features and outcome. *Blood* 1990; 75: 1024-1030

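### Randomisation is stratified by TBI, donor relationship and cell source, but no analysis in Section 14 uses these factors; using them would restore the nominal size of the superiority tests at almost no cost

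*Combined protocol and SAP*

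**What the plan says.** Section 5.1 sets 1:1 allocation in blocks of random size: "Randomization will be stratified by TBI in the preparative regimen (yes, no), donor relationship (related, unrelated), and source of hematopoietic cells". Each factor has two levels, so there are eight strata for 100 patients.

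Section 14 describes the analyses without these factors:

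- **Acute GVHD, sizing:** the criterion is "If the hazard ratio between treatment arms is at most 1.7", tested "using a one-sided non-inferiority log-rank test with 5% significance and 80% power".
- **Acute and chronic GVHD, analysis:** "Acute and chronic GVHD will be estimated using cumulative incidence methods and compared using the Pepe-Mori test".
- **Survival:** "compared between patients receiving Tac and MTX versus Tac, mini-MTX, and MMF using the log-rank test".
- **Hospital stay:** "Hospital stay will be compared between groups using the Wilcoxon rank sum test".
- **TPN and complications:** "TPN and 100-day incidence of complications will be compared using the Chi-square test".
- **Severe mucositis, neutrophil and platelet engraftment (primary):** a one-sided 5% level and 80% power are given, but no test is named.

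Sections 11.1.5 and 12 define the endpoints and add no adjustment.

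**The concern.** Balancing the arms on a prognostic factor makes the treatment difference less variable. A test that ignores the factor still uses the larger, unbalanced variance. Its true size then falls below the stated 5%, and some of the precision gained by stratifying is not used.

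The protocol itself points to one such factor. Section 1.1 gives clearly different acute GVHD rates by donor type, and Section 4.1 admits both types. For mucositis and engraftment no test is named, so whether to adjust could also be decided after the data are seen. At stake are a little efficiency and a prespecified choice. The validity of the results is not at stake.

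**Working it through.** **1. The plan's own figures**

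- *Mucositis, 41% to 16%:* n = [1.645√(2·0.285·0.715) + 0.842√(0.41·0.59 + 0.16·0.84)]² / 0.25² = 39.3, so 40 per group. With continuity correction it is 46.9, so 47, as stated. The sizing is for an unadjusted comparison.
- *Neutrophils:* no SD is stated. Fifty per group and a 4-day difference imply SD = 4 / [(1.645 + 0.842)√(2/50)] = 8.04 days.
- *Acute GVHD:* 4(1.645 + 0.842)² / (ln 1.7)² = 88 events. At 62% that needs 88/0.62 = 142 patients, or 71 per group, so the stated 45 is not reproduced. With 100 patients and 62 events, power is Φ(½√62·ln 1.7 − 1.645) = 67%. This is a separate matter; it is shown because it gives the starting power for step 5.

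**2. How conservative is an unadjusted test?**

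Inputs: 62% overall by day 60 (Section 14); related 40, 45 or 50% and unrelated up to 75% (Section 1.1). Because 75% is an upper bound and only 8/8 matches enter, an assumed 50% versus 65% is added. The unrelated share w is set so that the mixture is 62%, for example w = (62 − 40)/(75 − 40) = 0.629.

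The share of outcome variance due to donor type is R² = w(1 − w)(difference)² / (0.62·0.38). With balanced arms, the true two-sided size is about 2Φ(−1.96/√(1 − R²)).

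| Related vs unrelated | w | R² | Size by formula | Simulated, unadjusted | Simulated, three main effects |
|---|---|---|---|---|---|
| 40 vs 75% | 0.629 | 0.121 | 3.7% | 3.5% | 5.2% |
| 45 vs 75% | 0.567 | 0.094 | 4.0% | 3.9% | 5.4% |
| 50 vs 75% | 0.480 | 0.066 | 4.3% | 4.1% | 5.4% |
| 50 vs 65% | 0.800 | 0.015 | 4.8% | 4.8% | 5.4% |

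The simulation used 100 patients, eight cells, exponential times censored at day 60, only donor type prognostic, and 40,000 runs. Block sizes of 2 and 4 were assumed, since the plan does not give them. Repeat simulations gave 3.4% and 3.9% for the first row and 4.1% and 4.4% for the third.

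**3. Power for acute GVHD at hazard ratio 1.7, each test set to a true 5%**

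- *Log-rank-type test, unadjusted vs main effects:* 56.4 vs 59.1, 57.3 vs 59.8 and 58.4 vs 59.3%, a gain of 2.7, 2.5 and 0.9 points. At 50 vs 65% it is 60.0 vs 59.9%, no gain.
- *Pepe-Mori, no competing death:* 52.5 vs 53.9, 53.5 vs 54.3 and 53.1 vs 53.9%.
- *Pepe-Mori, 10% competing death:* 50.3 vs 51.2, 50.3 vs 51.1 and 51.1 vs 51.5%. Over both Pepe-Mori settings the gain is 0.4-1.4 points, and nil within 0.1 point at 50 vs 65%.

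**4. Other primary endpoints (factor effects assumed; the documents give none)**

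- *Mucositis and day-21 platelets, one-sided 5%, factor odds ratios 1 to 3:* chi-square size is 3.7-5.3%; Cochran-Mantel-Haenszel over four cells is 4.5-5.3%. The equal-size power change is −0.4 to +0.5 points.
- *Neutrophils, cell-source shift 0, 2, 4 or 6 days:* t-test size is 4.8, 5.0, 4.6 and 4.0%. Equal-size power, t-test vs three-factor linear model, is 80.2/80.1, 79.7/79.5, 81.3/81.2 and 83.7/83.8%.

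**5. Acute GVHD non-inferiority**

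- *If 1.7 is the overall ratio:* false non-inferiority with the unadjusted test is 4.0, 4.2, 4.4 and 4.9% (rows as in the table), so there is no inflation.
- *Power at a true ratio of 1, unadjusted vs main effects:* 68.2 vs 66.1, 67.9 vs 66.2, 67.5 vs 66.1 and 67.0 vs 66.0%. Adjustment costs 1.0-2.1 points.

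**6. Why not all eight cells?**

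The average is 100/8 = 12.5 patients per cell. With an assumed 25% TBI and 20% of one cell source, the smallest cell expects 1-2.4 patients. Four cells average 25.

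**The case against.** The strongest reply is that nothing goes wrong. Naming a plain log-rank, Wilcoxon, chi-square or Pepe-Mori test already specifies an unadjusted analysis. Such tests are valid, and with 100 patients in eight cells they are a defensible choice. The largest GVHD gain is for a two-sided superiority test that the plan does not contain, and it depends on an upper-bound 75%. For the other primary endpoints the gain at equal size is about nil.

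Most of this stands, and it is why the point is minor. It does not cover mucositis and engraftment, where no test is named, so silence cannot be taken as a choice of an unadjusted one.

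A reader might infer more: that the plain log-rank test inflates the false non-inferiority rate. That requires 1.7 to be a within-stratum ratio. The overall ratio would then be only 1.61-1.65 in the 75% scenarios, and the error 5.9-6.5% (5.3% at 50 vs 65%). It reaches about 7-10% only if all three factors are also given hazard ratios of 2 to 3. The documents support neither step. Section 14 pairs the ratio between arms with an unqualified log-rank test, which reads as the overall ratio, and it gives no factor effects. That the plan does not label the ratio is missing detail only.

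**Conclusion.** The point holds as a minor, nearly free improvement. Section 14 makes no use of the factors that Section 5.1 balances. The cost is mild conservatism: about 3.5-4.1% instead of 5% for an illustrative log-rank-type test on acute GVHD in the protocol's best case, and about 5% at 50 versus 65%. At equal size, adjustment is worth 0.4-1.4 power points for the planned Pepe-Mori test, at most about 3 for a log-rank-type test, and about nil for mucositis, platelets and neutrophils. For those three endpoints the benefit is a size nearer the stated 5% and a choice fixed in advance.

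No planned conclusion becomes invalid. The figures assume day-60 censoring, donor type as the only prognostic factor for GVHD, blocks of 2 and 4, and assumed factor effects for the other endpoints. Monte Carlo error is about 0.1-0.15 points for error rates and 0.25-0.3 for power.

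**What to change.** In Section 14:

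- **Time to engraftment:** compare the arms by regression with TBI, donor relationship and cell source as main effects.
- **Severe mucositis and platelet engraftment by day 21:** use a Cochran-Mantel-Haenszel test over TBI by donor relationship (four cells), and state that cell source is left out to avoid sparse cells.
- **Sensitivity:** report the unadjusted comparison for each of these endpoints, naming the test.
- **Acute GVHD non-inferiority:** keep the unadjusted log-rank test and state that 1.7 is the overall hazard ratio.

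The cost is wording only. The factors are already recorded at randomisation, and no patients or data are added. There are two statistical downsides. The four-cell test loses 0.1-0.5 power points if no factor is prognostic, and main-effects Cox tests run slightly above nominal, at 5.2-5.6%.

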6.0 TREATMENT PLAN

6.1 Agent Administration

6.1.1 Tacrolimus (Tac) Administration:

Patients in both group A and B will receive Tac 0.03 mg/kg/day intravenously beginning on day -1 or tacrolimus 0.03mg/kg/dose BID orally beginning on day -3. If Tac is administered intravenously, it will be given over 24 hours and will be converted to oral administration 2 times a day when the patient has engrafted and/or can tolerate oral medication.

Levels of Tac will be obtained to maintain a recommended target serum level of 5-15 mg/mL or per institution guidelines. Dose adjustments of Tac will be made according to Section 7.1.1 below.

In the absence of GVHD, Tac may start to be tapered approximately at day +100 and should be tapered off by day +180, per investigator's discretion.

6.1.2 Mycophenolate Mofetil (MMF) Administration:

Patients in group B only will receive MMF beginning on day +1. Patients ≥ 40 kg will receive MMF 1000 mg twice a day. MMF should be given orally twice a day. IV formulation may be used if the patient cannot tolerate oral route. Patients < 40 kg will receive MMF 45 mg/kg/day (15 mg/kg three times a day). MMF may be given orally or intravenously as per institutional protocol

In the absence of GVHD, MMF may be tapered after day +45 and stopped by day +100 at the discretion of the physician and per institutional guidelines for taper.

6.1.3 Methotrexate (MTX) Administration:

Group A

MTX will be given at 15 mg/m² IV on day +1. Then MTX will be given at 10 mg/m² on days +3, +6 and +11. Dose adjustments of MTX will be made according to Section 7.1.3 below.

If patient < 10 kg then MTX will be given at 0.5 mg/kg IV on day +1. Then MTX will be given at 0.33 mg/kg on days +3, +6 and +11.

Group B

MTX will be given at 5 mg/m² IV on days +1, +3 and +6.

If patient < 10 kg then MTX will be given at 0.17 mg/kg on days +1, +3 and +6.

6.2 General Concomitant Medications and Supportive Care Guidelines

Patients should receive full supportive care throughout the study including transfusions of blood and blood products, cytokines, antibiotics, antiemetics, Mesna, bladder washes and/or hydration to prevent hemorrhagic cystitis, etc. when appropriate.

The following therapies and/or medications should be avoided during the study period:

- Amiphostine
- IL-11(Neumega®)
- Sucralfate in suspension form (use of sucralfate tablets is not proscribed)
- Povidone-iodine rinses
- Other investigational agents
- Cytotoxic drugs other than those specified in the protocol (Exception: Intrathecal methotrexate or cytosinarabioside for subjects with central nervous system involvement)
- ATG suppression/Campath, or Rituximab as a prophylactic agent for GVHD (may only be used to treat aGVHD severity grades 3-4 refractory to steroids)

Patients will not be removed from study if taking one of the above medications but the medication, dose, dates taken, reason for taking it, etc. will be recorded.

Below are general guidelines but may vary depending on institutional and program guidelines.

6.2.1. Growth Factor Support - Colony stimulating factors (G-CSF)

No growth factor support will be routinely given unless indicated per standard institutional guidelines.

6.2.2 Anemia

Transfusions of red blood cells are indicated for the symptomatic management of anemia. An attempt will be made to maintain the hemoglobin > 8.0 g/dl. All blood products must be irradiated (1500 – 3000 cGy) and leukoreduced by filtration.

6.2.3 Thrombocytopenia

Prophylactic platelet transfusions should be given to maintain the platelet count $>10,000/\text{ul}$ or above a platelet level at which signs of bleeding are known to occur, whichever is greater. All aspirin-containing drugs are contraindicated.

6.2.4 Antimicrobial, Antifungal, Antiviral Prophylaxis

Antibacterial, antifungal, pneumocystis jiroveci, and antiviral prophylaxis is recommended and will be used according to institutional and program guidelines.

CMV surveillance and empiric treatment will be based on institutional and program guidelines.

6.2.5 Fever:

Aggressive diagnostic and therapeutic management of fever in the neutropenic patient is mandatory. The following are recommended guidelines for the management of fever, but may also be treated according to institutional and program guidelines. At the onset of fever (38°C), the patient should be thoroughly examined and cultured. Broad-spectrum antibiotics should be initiated to include coverage of gram-positive (including staphylococcus) and gram-negative (including pseudomonas) organisms. Voriconazole should be used empirically for persistent fevers (>3 days).

6.2.6 Mouth Care

A mouth care protocol per institution preference is recommended to be employed using a combination of mouthwash and other anti-bacterial solutions to minimize the risk of mucositis and dissemination of oral pathogens.

6.2.7 Venous access

Triple lumen Hickman catheters or Broviac catheters in pediatric patients, will be recommended to facilitate intravenous administration of drugs and the use of parenteral hyperalimentation.

6.2.8 Nutrition

Initiation of TPN will be left to the discretion of the attending physician; however general guidelines should be used as follows:

- In adult patients, it is recommended that the TPN support team should be consulted regarding potential initiation of TPN if:
 - there is less than 50% of enteral intake for > 7 days
 - patient has severe grade 3-4 WHO mucositis for > 5 days
- In pediatric patients, TPN is recommended if the child:
 - has less than 50% of enteral intake for > 3 days
 - has lost >10% of his admission weight
 - has severe grade 3-4 WHO mucositis that is expected to last more than 5 days
 - is showing signs of nutritional deficiency with a prealbumin < 15

6.2.9 Antiemetics

Antiemetics will be used based on institution and program guidelines. Standard antiemetic therapies include ondansetron, lorazepam, prochlorperazine and metoclopramide which can be considered either as scheduled or as needed medication.

6.2.10 Management of Acute Graft-Versus-Host Disease:

If acute graft-versus-host disease develops, the primary team will evaluate acute GVHD stage and grade and start the patient on prednisone or equivalent intravenous methylprednisone (MP) dose based on overall grade. Refer to Appendix I for Acute GVHD Grading Scale. Biopsy should be obtained whenever possible.

The goal of glucocorticoid therapy is to control the acute manifestations of GVHD and then to taper the doses of prednisone (or MP) as soon as possible. Literature demonstrates that prolonged use of high-dose glucocorticoids for the treatment of acute GVHD is associated with an increased risk for infection, relapse and death.

Treatment of mild acute GVHD

- includes rash < 50% of the total body surface area (skin < stage 3 and not progressing rapidly within 6-24 hours), anorexia, nausea, emesis, or diarrhea < 1.0 L/day (GI stage 1 or less) and no liver involvement (stage 0)
- can treat patient with prednisone at 1mg/kg (or equivalent MP), along with budesonide at 3mg orally twice daily and beclomethasone 1mg orally four times daily depending on patients upper and lower gastrointestinal symptoms

- recommended duration of 50 days with a taper over 1-2 weeks [14]
- Suggested duration and dosing of initial prednisone (or MP) treatment is at least 10 days with a subsequent taper according to patient response. If the patient has a rapid response to therapy, then the steroid taper may occur more rapidly every 3 days as suggested in Table A below:

TAPER SCHEDULE A (mild GI-tract GVHD with minimal diarrhea)

Day	AM dose (mg/kg)	PM dose (mg/kg)
1-10	0.5	0.5
11	0.25	0.25
13	0.125	0.125
15	0.0625	0.0625
17-79 *	Continue 0.0625	0
80	stop	0

* Day 50 Budesonide/belcomethasone may be stopped or tapered rapidly, over 1-2 weeks.

- If the patient has a slower response and improvement in his symptoms, it is recommended to taper every 5 days , as suggested in Table B below:

TAPER SCHEDULE B (mild GI-tract GVHD with 10-20 ml/kg diarrhea; max. 500-1000 ml/day)

Day	AM dose (mg/kg)	PM dose (mg/kg)
Before taper	0.5	0.5
1	0.5	0.4
6	0.5	0.3
11	0.5	0.2
16	0.5	0.1
21	0.5	0
26	0.4	0
31	0.3	0
36 – till day X	0.2	0
Day of taper	Mg/kg/day (AM dose only)	

6.3 Duration of Therapy

Study medications will be given up to 180 days. Adjustments will be made according to 7.1 below. In the absence of aGVHD, taper can begin at day 100 for Tac and Day 45 for MMF according to guidelines in 6.1.1 and 6.1.2 above.

After 180 days of therapy, it will be at the discretion of the investigators how these patients are to be treated if graft versus host disease develops. They may continue Tac and/or MMF or other therapeutic agents to treat graft-versus-host disease.

7.0 DOSING DELAYS / DOSE MODIFICATIONS

7.1 Adjustment of Study Medications:

Any GVHD prophylaxis medication change will be recorded along with the reason it was reduced or withheld.

7.1.1 Tacrolimus

Levels of tacrolimus will be drawn twice per week while hospitalized then weekly or monthly thereafter unless a change in medication or renal function might result in an acute change in level. The target serum level for tacrolimus is 5-10 mg/mL. Dose adjustments are based on clinical judgment of the treating physician after considering clinical toxicity, serum levels, GVHD, concomitant drug use and the rate of rise or decline of the serum level.

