9.2.3 Tacrolimus (NSC #77865)

Chemical name:	FK506
Formulation:	Capsule, oral: 0.5 mg, 1 mg, 5 mg. Injection, solution: 5 mg/ml (1 ml).

Toxicity:	Adverse reactions include back pain, constipation, diarrhea, dizziness, headache, joint pain, loss of appetite, nausea, stomach pain or upset, trouble sleeping, vomiting, weakness.
Mechanism of Action:	Binds to the FKBP-12 protein and forms a complex with calcium-dependent proteins, thereby inhibiting calcineurin phosphatase activity and resulting in decreased cytokine production. This agent exhibits potent immunosuppressive activity and prevents the activation of T-lymphocytes in response to antigenic or mitogenic stimulation.

10.0 **CORRELATIVE / SPECIAL STUDIES**

10.1 **Research Sample Repository**

The purpose of this correlative study is to improve our understanding of GVHD by storing samples of blood/tissue of the recipient to use in various laboratory studies.

10.1.1 **Background and Rational:**

GVHD is a complex disease which arises when donor T cells respond to genetically defined and disparate proteins on host cells; the most important of which are human leukocyte antigens (HLAs), which are highly polymorphic and are encoded by the major histocompatibility complex (MHC). GVHD is often associated with a graft versus leukemia (GVL) effect, but separating the two is often a challenge. The pathogenesis underlying GVHD is a complex, multi-step process. There are many factors which are not fully understood which determine whether GVHD occurs and the strength of the reaction. These include the type and properties of transplanted T cells, histocompatibility antigen mismatching, interactions between T cells and endothelial cells, signaling events occurring between immune cells, induction of pro-inflammatory cytokines, and amount of B lineage-specific progenitor cells. Acute GVHD requires the early trafficking of donor naive T cells to recipient secondary lymphoid tissue where they undergo activation and expansion, and their subsequent migration to target organs where they elicit injury [15-17]. The study of these processes through laboratory studies including the measurement of cytokine production and cytokine receptors, determination of hematopoietic cell subtypes by flow cytometry, and determination of HLA antigen types by genotyping may help elucidate and separate the detrimental and beneficial effects conferred by donor-derived T cells and improve our understanding of GVHD.

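### Sections 6.1.1 and 7.1.1 give different upper limits for the tacrolimus target level, both in a unit that the protocol's own doses cannot reach

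*Combined protocol and SAP*

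**What the plan says.** Section 6.1.1 covers both arms: "Patients in both group A and B will receive Tac 0.03 mg/kg/day intravenously beginning on day -1", or alternatively "tacrolimus 0.03mg/kg/dose BID orally beginning on day -3". It sets a "recommended target serum level of 5-15 mg/mL or per institution guidelines" and then refers the reader on: "Dose adjustments of Tac will be made according to Section 7.1.1 below".

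Section 7.1.1 states "The target serum level for tacrolimus is 5-10 mg/mL". It has no clause about institutional guidelines. It leaves adjustment to the treating physician's judgment and lists the serum level as one consideration beside toxicity, GVHD, other drugs and how fast the level is changing.

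Section 6.3 also points to Section 7.1 for adjustments. Section 9.2.3 lists the injection, before any dilution, at 5 mg/ml. No section assigns the two ranges to different periods, routes, ages or arms, and none gives another unit for the level.

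**The concern.** The two sections are linked by an explicit cross-reference, so both targets bear on the same decision. A clinician who reads Section 6.1.1 and follows its pointer arrives at a lower ceiling than the one just read. The unit raises a separate doubt: a serum target that starts at the strength of the undiluted injection cannot be what was meant.

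Tacrolimus is the component common to both regimens. Acute GVHD is a primary objective (Section 2.1) and is tested for non-inferiority (Section 14.0). Nephrotoxicity is a secondary objective (Section 2.2), and Section 8.1.1 names reversible renal insufficiency among the main toxicities of the drug. The target will be needed in practice: Section 6.2.5 recommends voriconazole for persistent fever, and the drug-interaction text in Section 8 describes a marked interaction between voriconazole and tacrolimus. Sections 8.3 and 8.4 refer to investigative sites in the plural, so different readers may apply different ceilings.

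**Working it through.** **Step 1. The ranges side by side.**

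| | Section 6.1.1 | Section 7.1.1 |
|---|---|---|
| Lower limit | 5 | 5 |
| Upper limit | 15 | 10 |
| Unit | mg/mL | mg/mL |
| Institutional alternative | yes | no |

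The narrower range lies inside the wider one, so levels of 5 to 10 satisfy both. The disputed band is above 10 and up to 15. Its share of the wider range is (15 − 10)/(15 − 5) = 0.5. The ratio of the upper limits is 15/10 = 1.5.

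**Step 2. Can the doses reach the printed level?** The doses come from Section 6.1.1: 0.03 mg/kg/day IV, or 0.03 mg/kg twice daily by mouth, which is 0.06 mg/kg/day. The documents give no body weight or blood volume for this purpose; 70 kg and 5 L (5,000 mL) are assumptions.

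- Daily IV dose: 0.03 × 70 = 2.1 mg.
- Daily oral dose: 0.06 × 70 = 4.2 mg.
- Drug needed for the lower limit: 5 mg/mL × 5,000 mL = 25,000 mg.
- In IV daily doses: 25,000/2.1 ≈ 11,900.
- In oral daily doses: 25,000/4.2 ≈ 5,950.

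**Step 3. Does the answer depend on weight or volume?** An upper bound on the level is the dose per kg divided by the distribution volume per kg, with complete absorption and no elimination. Body weight cancels, so the bound applies equally to children and adults. The distribution volume is not in the documents, so a range is used: 20 mL/kg (deliberately too small), 40 (about plasma), 70 (about blood) and 600 (about body water). For the whole course, Section 6.3 says "Study medications will be given up to 180 days". Counting from day −3 to day +180 gives 184 days, and at the oral starting dose without taper this is 0.06 × 184 = 11.04 mg/kg. All entries are in mg/mL; the factor in parentheses is 5 divided by the entry.

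| Volume (mL/kg) | One day IV | One day oral | Whole oral course, all retained |
|---|---|---|---|
| 20 | 0.0015 (3,333) | 0.003 (1,667) | 0.552 (9) |
| 40 | 0.00075 (6,667) | 0.0015 (3,333) | 0.276 (18) |
| 70 | 0.00043 (11,667) | 0.00086 (5,833) | 0.158 (32) |
| 600 | 0.00005 (100,000) | 0.0001 (50,000) | 0.0184 (272) |

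One day's dose falls about 1,700 to 100,000 times short of the lower limit. Even a full course with nothing eliminated falls about 9 to 270 times short. The stated target level cannot be reproduced from the protocol's doses.

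**The case against.** The strongest reply is that the target is soft. Section 6.1.1 calls its range recommended and allows institutional guidelines instead, and Section 7.1.1 rests adjustment on clinical judgment. No section makes a level of 10 or 15 a trigger for a dose change. This stands, and it limits the consequence. It does not reconcile the two ranges: the section named for adjustment states its target without the institutional alternative and lists the level among the things to weigh.

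A reader might infer that two written targets let the arms be run at different exposures and so bias the comparison. The documents do not support that. The same text covers both groups, and nothing ties either range to an arm. No blinding is described and the regimens visibly differ, so different management by arm is conceivable, but it is not demonstrated. Some latitude would also remain after the correction, because institutional guidelines and clinical judgment already allow it.

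Nor do the documents show how much an endpoint would move. They give no exposure-response figure for acute GVHD or nephrotoxicity at levels of 10 to 15 against 5 to 10, so no effect on power or error rates can be calculated.

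On the unit, it is fair to say that a target so far out of reach is more likely to be recognised as a misprint than dosed to. A text-reading error is also possible, though the same unit in two separate sections makes it less likely; the source file should be checked. Neither point settles which upper limit applies.

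**Conclusion.** Wrong as written. Two linked sections state different upper limits, 15 and 10, for the target level of a study drug given in both arms, and no text resolves the difference. This conclusion needs no assumption. The printed unit is unattainable on the protocol's own doses. The counts of about 11,900 IV or 5,950 oral daily doses rest on an assumed 70 kg and 5 L of blood, but the conclusion holds for either route, any weight and every volume from 20 to 600 mL/kg.

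The consequence is an erroneous operative dosing target and possible inconsistency in exposure management between clinicians or sites. The stronger inferences, that the arms are treated differently or that a primary result is biased, go beyond what the documents show.

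**What to change.** Reconcile Sections 6.1.1 and 7.1.1 to a single target range in a single unit, verified against the sponsor's source. State the range once and have the other section refer to it. Say explicitly how institutional guidelines relate to it: whether they may replace the range or only supplement it. Which range and which unit are right is for the sponsor's clinical team; nothing here favours either.

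The cost is a protocol wording amendment. It needs no new patients or data and no change to the sample size or analysis.
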